7.1 Study Procedures/Evaluations

The following study procedures will be completed:

Patient Subjects - LAB Protocol

Procedure and Evaluations	Purpose	Completed as Part of Study	When Performed	How Completed
Obtain Informed Consent	Complete informed consent	Yes	2 Weeks Prior (day- 14 +/-7 days) 1 Week Prior (day-7 +/-5 days)	Electronic consent obtained prior to initiating Pre-Visit Patient Survey Electronic signatures collected via REDCap Informed Consent Form when saliva specimen brought to office
Triage Case Reports	Collect COVID-19 screening data	Yes	Day Prior (day -2 +/- 2 days) Visit (day 1)	Data entered into REDCap via eCRF by Clinical Director, co-investigator or study staff member who interviews subject
Testing Case Reports	Collect information on outcomes of COVID-19 testing		Day Prior (day -2 +/- 2 days	Saliva Viral SARS-CoV-2 test results entered into REDCap via eCRF by Research Clinical Director, coinvestigator or study staff member based on testing result report obtained from secure e-mail.
Start-of-Visit Patient Survey Safety and Comfort COVID-19 Testing Preferences Perception of Importance Medical history Likelihood to report COVID-19 symptoms	Collect outcome measures	Yes	Visit (day 1)	Data entered via REDCap self- administered survey.
Dental Procedures Performed	Maintain patient oral health	NO	Visit	Completed by Dental Health Care Workers
PPE observed in office Environmental controls observed in office	Collect outcome measures	Yes	Visit (day 1)	Data entered via REDCap self- administered survey.
Patient Participation Questionnaire	Collect feasibility information on surveys and logistics	Yes	End of Study (Day 28)	Data entered via REDCap self- administered survey.

7.2 Laboratory Procedures/Evaluations

7.2.1 Clinical Laboratory Evaluations

Patient subjects will be tested for COVID-19 using a lab-processed saliva test.

	Patient LAB Test (PCR Viral Test)	
Test Description		
Company	Rutgers	
Sample collected via	Saliva collection tube with buffer	
What is being Tested	SARS-CoV-2 RNA	
Test Administration	Saliva collection performed by subject with saliva collection tube provided by a Research Clinical Director	
(specimen collection)		
Test Administration	RT-PCR test performed at ICPH-PHRI center, New Jersey Medical School, Newark, NJ	
(specimen processing)		
Results	Dichotomous (+ or -)	

With regard to the quality of the COVID-19 test specimen, the following will be used to assess the quality of the specimen.

	LAB Test
Indication of Proper	Accurate Diagnostic Labs will report if a sample is not able to be processed. This feedback will be used to identify insufficient
Processing	training or unanticipated problems.

Compliance with study protocols will be based upon the PI and the Chief of Clinical Protocol following the REDCap dashboard. The dashboard exhibits red indicators for instruments which have been started and not completed, yellow indicators for instruments which have been completed and not verified and green indicators for instruments which have been completed and reviewed. The PI or Chief of Clinical Protocol will be responsible for reviewing each instrument and changing the status from unverified to verified. Any issues with compliance with the study protocol identified by the PI or Chief of Clinical Protocol will be reviewed with the Research Clinical Director and be used to identify any unanticipated problems and develop/implement any necessary corrective action plans.

7.2.2 Specimen Preparation, Handling, and Storage

The following details specimen preparation, handling and storage.

	LAB Test
	LAD 165t
Sample Collection & Shipping	
Sample Collection Materials	Spectrum Saliva collection system via Accurate Diagnostics
Storage of Specimen Collection Supplies and POC	Clinical Research Center (D level of Dental School) and dental clinic dispensaries in the dental school
Test Kits	
Transport Media	Buffer solution
Packaging Specimen for Shipping	Sealed biohazard plastic bag
Sample Processing (Performing the Test)	
Processing Supplies	RNA extraction, followed by RT-PCR
Processing Time	About four hours
Conditions for Stability and Transport	
Condition	
Stability prior to Use	No special storage conditions required
Stability during shipping	Yes due to transport media
Storage prior to processing	PHRI Laboratory
Stability prior to processing	Stable at room temperature
Tracking	
Labeling	Specimen ID (bar code)
	Subject ID (bar code)

	Subject Name
	Date of Specimen
Tracking of Specimen Collection Kits	REDCap System and/or Excel Worksheet
Tracking of Tests Administered	Completion of REDCap COVID-19 Test Order and Results Form (which enables the generation of a
	Specimen Tracking Log)
Reporting of Results	
Time from specimen collection to reporting of	Results are normally available within 1 week
results	
Results Reporting	Via secure e-mail and then posted into REDCap via Research Clinical Director

7.2.3 Specimen Shipment

Saliva and immediately placed into a preservative and the tube with the sample then placed into a biohazard bag.

	LAB Test
Shipment Method and Frequency	Samples will be obtained from subjects Monday thru Thursdays. Saliva samples will be placed into the
	pick-box located on the B level of the MSB building.)
Packaging Specimen for Shipping	Sealed plastic biohazard bag
Shipping Address	Accurate Diagnostic Labs
	[name]
	[name]
Contact Information for Laboratory Personnel	Accurate Diagnostic Labs
	[contact]
Days and Times shipments are allowed	Monday thru Friday
	9:00 am to 5:00 pm
Labeling Requirements for Specimen Shipping	Subject Number, Subject Name, Birth Date and Collection Tube ID/Bar Code
Special Instruction for Specimen Collection	Subject should not eat or drink for 30 minutes prior to saliva specimen collection
Special Instructions for Specimens for Shipment	No special instructions
(i.e. dry ice, wet ice)	
Completion of Specimen-Tracking Log	Completion of REDCap COVID-19 Test Order and Results Form (which enables the generation of a
	Specimen Tracking Log)

9/1/2023

8 ASSESSMENT OF SAFETY

8.1 Definitions and Specifications of Safety Parameters

Safety monitoring for this study will focus on unanticipated problems involving risks to participants, including unanticipated problems that meet the definition of a serious adverse event.

Event	Definition	Form	Who completes REDCap form	Time Frame For Reporting to IRB	Additional Reports to
Unanticipated Problems	Any problem or event which in the opinion of the local investigator was unanticipated, reflects new or increased risk to the subjects and was possibly related to the research procedures. This includes any serious adverse event that is defined as an event which requires hospitalization and/or causes mortality	Unanticipated Problem Form	Site Director or Clinical Research Clinical Director	5 business days from the date of discovery 24 hours for hospitalization 24 hours for fatalities	Rutgers IRB
Protocol Deviations	Any change, divergence, or departure from the study design or procedures of a research protocol that is under the investigator's control and that has not been approved by the IRB.	Protocol Deviation/ Violation Form	Site Director or Clinical Research Clinical Director	5 business days from the date of discovery	Rutgers IRB
Protocol Violation	Any deviation from the IRB approved protocol that may affect the subject's rights, safety, or well-being and/or the completeness, accuracy and reliability of the study data	Protocol Deviation/ Violation Form	Site Director or Clinical Research Clinical Director	5 business days from the date of discovery	Rutgers IRB

Study procedures are limited to surveys and collecting capillary blood samples via finger prick. We therefore expect few, if any study related serious adverse events. In the rare event that a serious adverse event were to occur, an Unanticipated Problem form would be completed and SAE reporting timelines would be followed.

8.1.1 Unanticipated Problems

The Office for Human Research Protections (OHRP) considers unanticipated problems involving risks to subjects or others to include, in general, any incident, experience, or outcome that meets **all** of the following criteria:

- unexpected in terms of nature, severity, or frequency given (a) the research procedures that are
 described in the protocol-related documents, such as the IRB-approved research protocol and
 informed consent document; and (b) the characteristics of the subject population being studied;
- related or possibly related to participation in the research ("possibly related" means there is a
 reasonable possibility that the incident, experience, or outcome may have been caused by the
 procedures involved in the research); and
- suggests that the research places subjects or others at a greater risk of harm (including physical, psychological, economic, or social harm) than was previously known or recognized.

8.1.2 Serious Adverse Events

A serious adverse event (SAE) is one that meets one or more of the following criteria:

- Results in death
- Is life-threatening (places the subject at immediate risk of death from the event as it occurred)
- Results in inpatient hospitalization or prolongation of existing hospitalization.
- Results in a persistent or significant disability or incapacity
- Results in a congenital anomaly or birth defect

An important medical event that may not result in death, be life threatening, or require
hospitalization may be considered an SAE when, based upon appropriate medical judgment, the
event may jeopardize the subject and may require medical or surgical intervention to prevent one
of the outcomes listed in this definition.

If a SAE becomes known, the Research Clinical Director will immediately notify the study PI. The Research Clinical Director will record the event in the REDCap Unanticipated Problem Form based upon information obtained.

8.2 Reporting Procedures

8.2.1 Unanticipated Problem Reporting

Incidents or events that meet the Office of Human Research Protection (OHRP) criteria for UPs require the creation and completion of a UP report form.

OHRP recommends that investigators include the following information when reporting an adverse event, or any other incident, experience, or outcome as an unanticipated problem to the IRB:

- appropriate identifying information for the research protocol, such as the title, investigator's name, and the IRB project number;
- a detailed description of the adverse event, incident, experience, or outcome;
- an explanation of the basis for determining that the adverse event, incident, experience, or outcome represents an unanticipated problem;
- a description of any changes to the protocol or other corrective actions that have been taken or are proposed in response to the unanticipated problem.

To satisfy the requirement for prompt reporting, UPs will be reported that are not SAEs will be reported using the following timeline:

- Unanticipated problems that are SAEs will be reported to the IRB as soon as possible, and no later than within 24 hours of the investigator becoming aware of the event.
- Any other UP will be reported to the IRB within 5 business days of the investigator becoming aware of the problem.
- All UPs should be reported to appropriate institutional officials (as required by an institution's
 written reporting procedures), the supporting agency head (or designee), and OHRP within one
 month of the IRB's receipt of the report of the problem from the investigator.

All unanticipated problems will be reported to NIDCR concurrently with reporting to the IRB. These reports will be made to NIDCR's centralized reporting system via the Clinical Research Operations and Management Support (CROMS) contractor.

9/1/2023

9 STUDY OVERSIGHT

The investigator will be responsible for study oversight, including monitoring safety, ensuring that the study is conducted according to the protocol and ensuring data integrity. The PI will review the data for safety concerns and data trends at regular intervals, and will promptly submit reportable events to the IRB and NIDCR that arise during the conduct of the study.

9/1/2023

10 CLINICAL SITE MONITORING

No outside clinical site monitoring will be employed for this study. The Principal Investigator(s) and staff will closely monitor the subjects as they progress through the study. They will monitor and evaluate study processes and documentation based on the International Council for Harmonisation (ICH), E6: Good Clinical Practice guidelines (GCP), and internal quality management plans. The NIDCR reserves the right to conduct independent clinical site monitoring as necessary.

Expiration Date:

11 STATISTICAL CONSIDERATIONS

11.1 Study Hypotheses.

For this study, we hypothesize:

- Patients in offices with PBRN dentists and hygienists will be willing to participate
- Surveys will be easy to complete
- Testing protocols will be easy to complete

Analyses will be performed to test these hypotheses.

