POC Point-of-Care Veritor COVID-19 Test

PREDICT Pragmatic Return to Effective Dental Infection Control through Triage and

Testing

PS Project Scientist, NIDCR, NIH

QA Quality Assurance
QC Quality Control
QoL Quality of Life

РΟ

SAE Serious Adverse Event/Serious Adverse Experience

SOP Standard Operating Procedure

UP Unanticipated Problem

US United States

WHO World Health Organization

Expiration Date:

PROTOCOL SUMMARY

Title: Pragmatic Return to Effective Dental Infection Control through Triage and

Testing

Précis: We will conduct a feasibility study to develop and test out procedures for

improved triage and COVID-19 testing of patients in dental practices to improve patient safety. This is one of several feasibility studies to be conducted in Rutgers dental clinics and in dental offices which participate in the National Dental Practice Based Research Network (PBRN). These studies will assess the feasibility of implementing COVID-related

procedures in the dental setting and may provide preliminary data to inform

a larger network-wide study grant application.

Objectives: Primary: The primary objective of this study is to determine patient

willingness to participate in a study and to test survey instruments and logistics developed for a NIH clinical study evaluating the impact of COVID-

19 testing and enhanced triage in dental offices.

Population: This study will take place at Rutgers University School of Dental Medicine.

Up to twenty (20) patients will be recruited in the Rutgers School of Dental Medicine's dental clinics. Only adults who are patients who are scheduled

for dental appointments will be recruited.

Number of Sites: One (1)

Description of Lab-processed saliva tests (Viral PCR SARS-CoV-2 tests) will be

administered to patients coming to the school for care. In addition, the use

of pulse oximeters will be added to the patient COVID-19 symptom triage

protocol.

Study Duration: Twelve (12) months

Subject Participation

Duration:

Intervention:

[figure not shown]
Two (2) weeks.

Estimated Time to Complete Enrollment:

Six (6) months

Expiration Date:

Schematic Study Design for Patient Subjects:

Expiration Date:

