4 STUDY DESIGN

Description: This study will assess the feasibility of implementing one COVID-related testing procedure in the dental setting. Results from this study may provide preliminary data to inform a larger network-wide study grant application.

Study Population: The study population for this study will be patients seen at the Rutgers School of Dental Medicine.

Important Outcomes: For this study, important outcomes include percent of patients willing to participate and percent completing the protocol.

Single or Multicenter: Single- this study will utilize the Rutgers School of Dental Medicine's Newark facility.

Number of Study Groups/Arms: One (1)

Expected Duration of Subject Participation: Subjects will be actively participating in the study for 2 weeks.

Sequence of Procedures and Duration of Study Period: Consent Process

About two weeks prior to their scheduled dental visit, patients will be contacted by the dental office to determine their willingness to participate in the study. Patients who indicate interest will be sent an email link, which opens the consent. The consent will clearly outline participant expectations and offer the opportunity for potential participants to contact the office for more information as needed. Participants who fully understand the study and elect to participate will affirm their willingness to participate by clicking the "I agree to take part in this study" button at the end of the consent form. Once in the office to provide their saliva sample, patients will also be asked to provide signed informed consent.

Study Procedures

Study participants will be asked to do the following:

- Two weeks before the dental visit
 - o Complete an electronic survey: Patient Pre-Visit Survey
 - Questions explore perceptions of safety and comfort, reasons for delaying dental care, concerns about returning to dental care, safety precautions valued, importance of triage and testing, and demographics
 - Launched automatically after the completed consent
 - Receive a saliva collection kit by mail
- One week before the dental visit
 - o Complete a COVID-19 saliva test
 - Spit into a tube
 - Package as directed
 - Drop off the completed test kit at the dentist's office
- Day prior to the dental visit
 - Undergo a COVID-19 triage screening over the phone*
 - Screening includes symptom questions (presence or absence of):
 - fever or chills
 - cough
 - shortness of breath or difficulty breathing
 - fatigue
 - muscle and body aches

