5 STUDY POPULATION

5.1 Participant Inclusion Criteria

A **Patient** must meet all of the following criteria to be eligible to participate in the study:

- Be a patient being treated at the Rutgers School of Dental Medicine
- Be 18 years or older
- Be able to understand the informed consent.
- Provide signed and dated informed consent form
- Be able to understand all instructions for data collection instruments in English
- Be willing and able to comply with all study procedures, including having a COVID-19 test performed

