5.3 Strategies for Recruitment and Retention

Target Sample Size: 20 patients.

Target Sample Size by Gender, Race, Ethnicity, and Age: Study population will be drawn from patients at the Rutgers School of Dental Medicine. It is estimated that about ½ will be female, ½ male. All will be English speaking. Age range will be between 18 and 100 years of age. Racial and ethnicity background will be reflective of the respective populations at the Rutgers Schools of Dental Medicine with about 52% being African American and 33% Hispanic.

Study Population: The patient study population will be drawn from outpatient dental clinics located at Rutgers University School of Dental Medicine.

Inclusion of Women and Minorities and Individuals of All Ages:

Women: Women will be included in this study. Pregnant women are eligible to participate.

Minorities: Minorities will be included in this study.

Recruitment Strategies: Patients treated in the Rutgers School of Dental Medicine's Oral Medicine clinic will be recruited. If 20 patients cannot be recruited in the Oral Medicine clinic, recruitment will expand to the school's other clinics. It is not anticipated that there will be difficulties recruiting sufficient patients.

Retention: In order to minimize loss of study participants and/or incomplete data collection, the following activities will take place:

- The Research Clinical Director will work with the co-investigators responsible for recruiting subjects and completing surveys.
- Participants will receive compensation.

Compensation and Scheduled Payments: Patients who complete the protocol, including the post-visit survey will be provided \$100.

Additional Plans to Minimize Loss of Follow-up and Missing Data: The following will minimize loss of follow-up and/or missing data:

• When appropriate, REDCap survey data fields are set to "required".

REDCAP validation rules on data fields to limit responses to valid responses

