11.3 Final Analysis Plan

Data to be collected includes:

Item	Type of Variable
Willingness to Participate	 Willingness to participate (Binary – Yes/No)
Patient willingness to participate	
Triage Survey	Ease of Administration (3 point Likert Scale) Very easy to complete survey due to administration method Easy to administer complete survey due to administration method Not easy to complete survey due to survey administration method Completeness (Binary – Yes/No) Question understandability (3 point Likert Scale) Very clear to understand Understandable with some clarification provided by the administrator Not clear to understand
Safety Perception Survey	
Start-of-Visit Patient Survey End-of-Visit Patient Survey	Administration method (3 point Likert Scale) Very easy to complete survey due to administration method Easy to complete survey due to administration method Not easy to complete survey due to administration method
	 Completeness (Binary – Yes/No)
	 Question understandability (3 point Likert Scale) Very clear to understand Understandable with some clarification provided by the administrator Not clear to understand
Testing Logistics	Specimen Collection (3 point Likert Scale)
LAB – saliva SARS-CoV-2 viral test	 Very easy to collect Easy to collect Not easy to collect Specimen preparation for shipping (3 point Likert Scale) Very easy to prepare Easy to prepare Not easy to prepare Specimen storage (Binary – Easy/Not Easy) Easy to Store Not easy to store

	Timeliness of results (3 point Likert Scale) Very timeless access to results Timely access to results Access to results not timely Reporting of results (3 point Likert Scale) Very easy to access results Easy to access results Not easy to access results	
Testing Case Report	 Completeness (Binary – Yes/No) 	

Descriptive statistics (frequencies) for all variables will be analyzed.

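### Section 11.1 promises to test willingness in PBRN offices, but the study recruits only Rutgers dental school patients and Section 11.3 plans frequencies with no test, reference proportion or interval

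*Combined protocol and SAP*

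**What the plan says.** **Hypotheses.** Section 11.1 gives three for this study: "Patients in offices with PBRN dentists and hygienists will be willing to participate", that surveys will be easy to complete, and that testing protocols will be easy to complete. It adds: "Analyses will be performed to test these hypotheses".

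**Who is recruited.** Section 4: "The study population for this study will be patients seen at the Rutgers School of Dental Medicine". Section 5.1 makes it an inclusion criterion: "Be a patient being treated at the Rutgers School of Dental Medicine". Section 5.3: "The patient study population will be drawn from outpatient dental clinics located at Rutgers University School of Dental Medicine". If the Oral Medicine clinic falls short, Section 5.3 extends recruitment to the school's other clinics and no further. The Protocol Summary gives one site and up to 20 patients.

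**The wider programme.** The Protocol Summary says: "This is one of several feasibility studies to be conducted in Rutgers dental clinics and in dental offices which participate in" the network. Rutgers clinics and PBRN offices are thus listed as separate settings.

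**Analysis.** Section 11.2 says that no sample size calculation is being done. The only analysis statement in Section 11.3 is "Descriptive statistics (frequencies) for all variables will be analyzed".

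**Measures.** Section 3.0 defines willingness as those agreeing relative to all those asked, and defines ease as a percentage of patients. Section 11.3 lists willingness as a yes/no item and most ease items on three levels, for example "Very easy to collect Easy to collect Not easy to collect"; specimen storage is a two-level item.

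**The concern.** Willingness is part of the primary objective, and the Protocol Summary says that the feasibility results may inform a larger network-wide application. If Section 11 stands, a percentage from one dental school could be reported under a hypothesis about PBRN offices and described as tested. Neither description would be accurate: the setting differs, and a frequency table contains no test.

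A smaller gap goes with this. Section 3.0 wants one percentage for ease, Section 11.3 collects three levels, and no rule links them. Nor is it stated whether that percentage is taken over respondents or over everyone enrolled.

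**Working it through.** **1. Population.**

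| Item | Setting | Where |
|---|---|---|
| Hypothesis 1 | Offices with PBRN dentists and hygienists | Section 11.1 |
| Number of sites | One | Protocol Summary, Section 4 |
| Eligibility | Patient of the Rutgers dental school | Section 5.1 |
| Fallback recruitment | Other clinics of the same school | Section 5.3 |
| Programme | Rutgers clinics and PBRN offices, listed separately | Protocol Summary |

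The documents never state that the Rutgers clinics are PBRN offices, and recruitment is not defined by network membership.

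**2. Test.** A one-sided exact test of a proportion needs a reference value p0 and a critical count r, with error rate P(X ≥ r | n, p0). The plan gives neither p0 nor r nor an error rate, so there is no figure of the plan's own to reproduce. The result would depend on the missing value. With n = 20 and an error rate of at most 0.05, the smallest count that rejects p0 (all p0 values assumed) is:

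- p0 = 0.50: 15 of 20 (error rate 0.021)
- p0 = 0.70: 18 of 20 (0.035)
- p0 = 0.80: 20 of 20 (0.012)

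A result of 16/20 would therefore support or fail to support a hypothesis depending on a number that the plan does not contain.

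**3. Precision for willingness.** The denominator is all patients asked (Section 3.0), not the enrolment target. The number asked is not planned, so the values of n below are assumptions, with x = 20 enrolled. The exact (Clopper-Pearson) 95% limits are beta quantiles:

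- lower = Beta(0.025; x, n − x + 1)
- upper = Beta(0.975; x + 1, n − x)

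| Asked (assumed) | Willing | Exact 95% CI |
|---|---|---|
| 25 | 20/25 = 80% | 59% to 93% |
| 30 | 20/30 = 67% | 47% to 83% |
| 40 | 20/40 = 50% | 34% to 66% |
| 60 | 20/60 = 33% | 22% to 47% |

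These limits treat the number asked as fixed. If asking stops at the 20th agreement, the lower limit is unchanged and the upper becomes Beta(0.975; x, n − x). At 25, 40 and 60 asked that is 92.9%, 65.2% and 45.6%, against 93.2%, 66.2% and 46.7%. The difference is about one point at most.

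**4. Ease.** Take an assumed split of 8 very easy, 8 easy and 4 not easy. Counting the top two levels gives 16/20 = 80% (56% to 94%); counting only the top level gives 8/20 = 40% (19% to 64%). The denominator also matters. If 4 of 20 enrolled gave no rating (assumed), 14 favourable ratings are 14/16 = 88% of respondents but 14/20 = 70% of those enrolled.

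**5. Number of ease respondents.** This cannot yet be judged. Section 4, Section 6.1 and Appendix A put the Patient Participation survey at the Day 1 visit; the table in Section 7.1 puts it at Day 28. Under Section 7, a patient who tests or triages positive is not seen at the scheduled visit. Whether and when that patient rates the logistics depends on which timing applies.

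**The case against.** The best defence is that this is a 20-patient feasibility study meant to refine logistics. Descriptive frequencies suit it, no decision depends on a test, and the Rutgers setting is stated so often that few readers would be misled. That stands as a defence of Section 11.3. It does not rescue Section 11.1, which speaks of this study and still names another setting and promises tests.

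It may also be said that some Rutgers clinicians could be PBRN members. The documents do not exclude this, but they do not say it, and eligibility does not use it.

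Three stronger readings are tempting, and the documents do not support them:

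- *Ease is undefined.* Section 11.3 labels the response levels, and a frequency table of a three-level item shows all three. On a plain reading, very easy is a kind of easy. The contrast of 80% with 40% arises only if a report collapses the scale without saying how. Only the collapsing rule and the denominator are missing.
- *Non-response would be hidden.* Section 3.0 makes study and survey completion outcomes, and Section 13 says that the number or percentage of incomplete forms will be analysed.
- *The analysis plan is missing.* Section 15.4 points to a Section 12.4 that does not exist, but Section 11.3 is titled as the final analysis plan. This is a clerical slip.

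**Conclusion.** The concern holds for the mismatch between Section 11.1 and the rest of the plan. The design does not address hypothesis 1 as worded, and none of the three hypotheses is tested. This rests on the text alone and needs no assumption.

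For size, an interval for willingness with 20 enrolled would span roughly 25 to 36 percentage points across the assumed range of 25 to 60 asked (for example 34% to 66% at 40 asked). That is adequate for feasibility, but it describes Rutgers clinic patients only. The numbers asked, the ease split and the count of non-respondents are illustrations, since the documents give no expected values.

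A reader might infer that the study needs a formal test, a success threshold or a larger sample. It does not: an estimation aim needs no threshold, and the sample is not presented as powered. The correction should be made because it narrows what may be concluded, but the study remains usable as designed.

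**What to change.** 1. **Section 11.1, hypothesis 1.** Restate it for patients of the Rutgers School of Dental Medicine clinics, and say that willingness in PBRN offices is not estimated here.
2. **Section 11.1, aim.** Replace the promise to test the hypotheses with a statement that the corresponding proportions will be estimated.
3. **Section 11.3.** Report each proportion with its count, denominator and exact (Clopper-Pearson) 95% CI. For willingness, carry over the Section 3.0 denominator of all patients asked, and keep a count of them.
4. **Ease.** Wherever a single percentage is given, state that it combines the very easy and easy levels, among respondents, and show the number enrolled beside it.
5. **Timing.** Reconcile the Day 1 and Day 28 entries for the Patient Participation survey before judging how many patients will supply ease ratings. The reference in Section 15.4 can be corrected to Section 11.3 in the same edit.

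The cost is a few sentences and a count of patients asked, with no new data from participants. The downside is a narrower claim and intervals that look wide.
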